# 13.5.3 Analysis of other efficacy endpoints

All results of patient assessment of pain intensity in the assessed joint on VAS will be presented by measurement points and treatment groups using descriptive statistics.

For all patient assessments of pain intensity in the assessed joint on VAS, pain intensity versus time by the treatment groups will be plotted.

Model means of changes from baseline in pain intensity in the assessed joint on VAS and confidence intervals for pairwise differences between each RPH-104 treatment group and the Voltaren® (diclofenac) group will be presented for each measurement point using repeated measures ANOVA. A model for assessing differences between groups will be selected after assessment of the primary endpoint.

The patient's response to therapy will be presented as frequency tables by assessment point and therapy group.

The results of assessing the degree of swelling, tenderness, erythema and movement restriction in the assessed joint will be presented as frequency tables by points of assessment and treatment groups.

Changes in the degree of swelling, tenderness, erythema and movement restriction in the assessed joint from baseline will also be presented as continuous variables using descriptive statistics by measurement points and treatment groups.

Graphs of changes in the parameters versus time by the treatment groups will be plotted for changes in the degree of swelling, tenderness, erythema and movement restriction in the assessed joint from baseline.

The analysis of time to 50% reduction in pain intensity in the assessed joint will be carried out using the Kaplan-Meier method. Comparison between groups will be carried out using a log-rank test.

CONFIDENTIAL P. 75 of 84

More details on the efficacy endpoint analysis methods will be described in the statistical analysis plan, which will be developed and approved prior to the data lock point for interim analysis.

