	
 
Change in serum cytokine (IL-1α, IL-1β, IL-1RA, IL-6, IL-8, TNF-α) levels at 24, 72 hours, 5, 6, 15, 29 and 45 days after start of the investigational product therapy compared to baseline.
 

Safety variables:	Adverse events, laboratory results, vital signs, physical examination findings, ECG findings.
Statistical methods:	Data analysis
	Descriptive statistics of continuous variables will be presented using means,

CONFIDENTIAL P. 16 of 84

Sponsor Name: R-Pharm International LLC
Investigational medicinal product provided by the
Sponsor:
RPH-104/L04018
Name of the active ingredient:
RPH-104/L04018

median, 25th and 75th percentiles, standard deviation, minimum, maximum, number of observations available. Categorical data will be presented as absolute and relative values for each category. Time to event parameters will be plotted using Kaplan-Meier curves.

Efficacy analysis

The primary efficacy variable will be analyzed by analysis of covariance using baseline and treatment group as covariates. Other continuous efficacy variables will be analyzed using repeated measures ANOVA. Efficacy variables representing time to event will be compared using a log rank test.

The pharmacokinetic, pharmacodynamic and immunogenicity parameters of RPH-104, as well as safety of the therapy with the investigational products will be assessed using descriptive statistics methods.

Interim data analysis

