# Analysis of pharmacodynamic data

The levels of hs-CRP, serum amyloid protein A and cytokines will be presented by measured parameters, measurement points and treatment groups using descriptive statistics.

For hs-CRP, serum amyloid protein A, and cytokines, graphs of changes in the concentration of these substances versus time for the treatment groups will be plotted.

Model mean changes (least squares means) in hs-CRP, serum amyloid protein and cytokine levels from baseline and confidence intervals for pairwise differences between each RPH-104 group and Voltaren® (diclofenac) group will be presented for each parameter and measurement point using ANCOVA with the baseline value of the parameter as a covariate.

All measured hs-CRP, serum amyloid protein A and cytokine levels will be presented as lists.

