# Secondary efficacy endpoints

- Change in pain intensity in the assessed joint at 15, 30, 45 minutes, 1, 1.5, 2, 4, 8, 24, 48, 72 hours, on days 5, 6, 10, 15, 18, 22, 29 and 45 after start of the investigational product therapy compared to baseline (as measured on VAS).
- Proportion of patients who rated the response to the investigational product therapy as "Excellent" or "Good" at 15, 30, 45 minutes, 1, 1.5 hours, 2, 4, 8, 24, 48, 72 hours, on days 5, 6, 10 15, 18, 22, 29, and 45 after initiation of the investigational product therapy;
- Change in the degree of swelling, tenderness, erythema in the assessed joint at 24, 48, 72 hours, on days 5, 6, 10, 15, 18, 22, 29 and 45 after start of the investigational product therapy compared to baseline;

CONFIDENTIAL P. 74 of 84

- Change in movement restriction in the assessed joint at 24, 48, 72 hours, on days 5, 6, 10, 15, 18, 22, 29 and 45 after start of the investigational product therapy compared to baseline:
- Time to 50% reduction in pain intensity in the assessed joint relative to the baseline level according to the VAS;
- Time to use of the rescue medication
- The proportion of patients who received the rescue medication within 72 hours of starting the investigational product therapy and over the entire treatment period;
- Changes in the health assessment questionnaire scores 2, 4, and 6 weeks after start of the investigational product therapy compared to baseline.

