## 13.5.2 Analysis of the primary efficacy endpoint

The results of the primary endpoint assessment will be presented using descriptive statistics.

The confidence intervals for the change in pain intensity on VAS in each treatment group will be calculated by ANCOVA using the baseline values and treatment group as covariates.

As supplemental analyses for the primary endpoint, model mean values (least squares means) of changes in pain intensity and confidence intervals for pairwise differences between each RPH-104 therapy group and Voltaren® (diclofenac) group will be presented using ANCOVA model with factors of the baseline pain intensity score and baseline body mass index (BMI) as covariates.

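### The repeated measures model for VAS pain differences at 19 time points names no baseline pain term, so chance baseline imbalance can enter the estimates and precision is lost

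*Combined protocol and SAP*

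**What the plan says.** The secondary endpoint list in Section 13.5.1 begins "Change in pain intensity in the assessed joint at 15, 30, 45 minutes, 1, 1.5, 2, 4, 8, 24, 48, 72 hours" and continues with eight study days from Day 5 to Day 45. For these, Section 13.5.3 presents model means of change from baseline, and confidence intervals for each RPH-104 dose against diclofenac, which "will be presented for each measurement point using repeated measures ANOVA". The synopsis agrees: "Other continuous efficacy variables will be analyzed using repeated measures ANOVA". Neither place names a covariate.

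Baseline is named in the other comparative models. For the primary endpoint, Section 13.5.2 says that the group intervals "will be calculated by ANCOVA using the baseline values and treatment group as covariates", and that the pairwise differences are obtained "using ANCOVA model with factors of the baseline pain intensity score and baseline body mass index (BMI) as covariates". Section 13.4 gives the pharmacodynamic differences "for each parameter and measurement point using ANCOVA with the baseline value of the parameter as a covariate".

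Two further sentences in Section 13.5.3 matter. One reads "A model for assessing differences between groups will be selected after assessment of the primary endpoint". The other reads "More details on the efficacy endpoint analysis methods will be described in the statistical analysis plan", meaning a separate document due before the data lock for the interim analysis. That document is not part of the text reviewed.

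**The concern.** The same outcome on the same patients is adjusted for baseline pain at 72 h in the primary analysis, but as written it is not adjusted at the 19 secondary time points, one of which is again 72 h. Patients enter with pain anywhere from 50 to 100 mm, arms have 14 or 15 patients, and Section 6.3.1 mentions no stratification on pain. Arms will therefore differ in baseline pain by chance.

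Change from baseline does not remove that difference. Once an attack has resolved, a patient who started higher has a larger fall simply because of the higher start. An arm that began with more pain can then look more effective. The contrasts at stake are those on onset and durability across doses, which this study interprets through confidence intervals rather than tests (Section 13.7).

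**Working it through.** **Inputs from the plan.** SD of change at 72 h is 26 mm, with 14 patients per arm and 15 in the 4 mg arm (13.1.2). The level is two-sided 5% (13.1.4). Baseline pain is 50 to 100 mm (7.2). There are 11 time points to 72 h plus 8 later days, 19 in all (13.5.1).

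**Assumed, because the documents do not give them.** Baseline SD is 8 to 14.4 mm; the upper value is a uniform spread over the entry range, 50/√12. The slope b of follow-up pain on baseline pain runs from 0 to 1. The 26 mm is stated for 72 h only, so the interval widths below apply to a time with that spread.

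**The plan's own figures.** Group interval: t(13) × 26/√14 = 15.01 mm either side, 30.02 mm in full, which matches the stated 30 mm read as a full width. Smallest significant pairwise difference: t(26) × 26 × √(2/14) = 20.20 mm, which matches the stated 20 mm.

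**Chance gap in baseline pain.** SD of the gap between two arms of 14 = baseline SD × √(2/14): 8 × 0.378 = 3.0 mm, and 14.4 × 0.378 = 5.4 mm.

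**How much enters the difference.** If follow-up = a + b × baseline + error, then change = a + (b − 1) × baseline + error. An unadjusted difference therefore shifts by (1 − b) mm for each mm of gap. For a gap of one SD:

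- b = 1: 0 mm
- b = 0.5: 1.5 to 2.7 mm
- b = 0: 3.0 to 5.4 mm

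With baseline in the model the shift is about 0.

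**Precision.** Unadjusted half-width: t(79) × 26 × √(2/14) = 19.56 mm. The share of variance in change explained by baseline is R² = ((1 − b) × baseline SD/26)². Adjusted half-width: t(78) × 26 × √(2/14) × √(1 − R²) × √(1 + 1/77).

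| b | Adjusted half-width, baseline SD 8 | Adjusted half-width, baseline SD 14.4 |
|---|---|---|
| 0 | 18.74 mm | 16.39 mm |
| 0.5 | 19.46 mm | 18.92 mm |
| 1 | 19.69 mm | 19.69 mm |

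**Simulation.** The set-up was 10,000 trials of 85 patients in six arms, with baseline uniform on 50 to 100 mm and SD of change 26 mm. For b = 0, 0.5 and 1, the unadjusted difference moved by 1.0, 0.5 and 0 mm per mm of baseline gap, in the direction that favours the arm with the higher baseline. With baseline in the model it moved by about 0. Coverage of the unadjusted 95% interval over all trials was 95.0%, 95.1% and 94.9%. In the roughly 35% of trials with a gap above 5 mm, it was 91.0% at b = 0 and 94.6% at b = 0.5 and b = 1.

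**Dilution by BOCF.** A patient set back to baseline has zero change, so for that patient b is 1. If a share p of patients is carried in this way and the others have fully resolved (b = 0), the shift is (1 − p) per mm: 0.9, 0.8 and 0.7 at p = 10%, 20% and 30%. With an assumed mean baseline of 70 mm and SD of 13 mm, the variance of change is (1 − p) × 169 + p(1 − p) × 4900, so the SD is 24, 30 and 34 mm. Baseline explains (1 − p)² × 169 of that variance: 23%, 12% and 7%.

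**The case against.** The strongest reply is that silence is not a decision. Section 13.5.3 defers the choice of model and Section 13.1.7 promises a separate analysis plan, so a baseline term may yet be included. That stands: the term is unstated, not ruled out. It is also a reason to settle the term now, because a model chosen after the primary result is known is weakly pre-specified.

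Three stronger readings are tempting, and the documents do not support them.

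- A reader might infer that leaving out baseline makes the intervals invalid. It does not. Coverage is nominal over randomizations, and the loss is in precision and in trials with a sizeable gap.
- A reader might infer that intervals must be too narrow at 72 h and too wide in the first minutes, because classical repeated measures ANOVA pools one error variance over all times. That is a separate mechanism and could happen. Pooled SDs of 17.7 to 25.3 mm against 26 mm would give 82 to 94% coverage at 72 h, but those SDs come from assumed profiles of spread over time. The plan states no covariance structure.
- A reader might infer that late contrasts mainly compare baseline pain. If the BOCF rule of Section 13.1.6 is applied at these times, late change is a mixture of zero and minus baseline, and the share of rescued patients drives much of the spread.

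It is also fair to say that the study is exploratory and that 72 h has a designated primary analysis, so a second longitudinal estimate at 72 h is supportive output rather than a rival result. Both points limit the consequence. Neither is a reason to leave out a measured predictor.

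**Conclusion.** The point holds as a gap in specification with a modest, calculable cost. The named method lists no baseline pain term for the 19 VAS contrasts, and this differs from Sections 13.5.2 and 13.4. On the assumed baseline SD of 8 to 14.4 mm, a one-SD chance gap moves a contrast by up to 3.0 to 5.4 mm, which is 15 to 27% of the plan's 20 mm difference. The shift is near zero in the first hours if pain still tracks baseline, and smaller than the maximum at late times if BOCF zeros are present. At SD 26 mm, adjustment shortens the half-width by 4 to 16% at b = 0 and by about 0.5 to 3% at b = 0.5; at b = 1 it adds about 0.1 mm. The estimates are unbiased over randomizations and the unadjusted intervals are valid on average. Whether widths would be wrong at individual times cannot be judged until a covariance structure is stated.

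**What to change.** In Section 13.5.3 and the synopsis, replace the bare reference to repeated measures ANOVA for VAS pain with one of two specified models, and remove the sentence that leaves the choice until after the primary result.

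- A longitudinal model for change with treatment, time, treatment-by-time, baseline pain and baseline-by-time, and a separate variance at each time. Name the correlation structure too: a fully unstructured matrix for 19 times has 19 × 20/2 = 190 parameters, with 85 patients planned.
- If BOCF is applied at every time point, ANCOVA at each time point with treatment and baseline pain, as Section 13.4 already does. Section 13.1.6 states BOCF only for the main efficacy analysis, so its use at the other times must be written down. Without it, this option would drop patients from later time points after rescue.

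State that the 72 h pairwise contrast from Section 13.5.2 is the reference result.

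The cost is wording and one baseline slope per time point. Baseline pain is already recorded within an hour before randomization, so no new data are needed.

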# 13.6 Safety data analysis

Safety parameters include the frequency and severity of adverse events, the frequency of serious adverse events, vital signs, 12-lead ECG findings, echocardiography findings, physical examination findings, complete blood count, blood chemistry tests, and urinallysis results. The safety population will be used to present the safety data for the study therapy.

#### 13.6.1 Adverse events

Adverse events occurring starting from the time of investigational product administration (start of use) until 45 days after the investigational product administration will be considered treatment-emergent adverse events.

Serious adverse events developing between the signing by the patient of the Informed Consent Form for participation in this study and the administration of the investigational medicinal product will be regarded as pre-treatment SAEs.

Adverse event data will be coded using the last version of the MedDRA medical terminology. Frequency rates of adverse events during the study therapy will be calculated for each organ system, by primary diagnosis, investigational product dose, and absolute and relative amounts of patients developing adverse events. Summary data reflecting the severity of adverse events will be presented by organ system and primary disease. Adverse events related to the investigational product ('possibly related,' 'probably related,' and 'definitely related') will be presented separately.

Summary data reflecting withdrawals from the study due to adverse events will be presented by organ system and primary disease.

Serious adverse event data will be presented as listings and summary data by organ system and primary disease.

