### 4.3.2 Clinical pharmacology trials

Pharmacokinetics of RPH-104 in humans

At the time of writing this protocol, data on the pharmacokinetics of RPH-104 were available for a single subcutaneous injection in healthy volunteers at doses of 4 and 20 mg. The results of evaluation of pharmacokinetic RPH-104 parameters from phase 1 studies in healthy volunteers are provided in Table 4.1 below.

Table 4.1 Pharmacokinetic parameters of RPH-104 after a single subcutaneous injection in healthy volunteers

PK parameters/RP H-104 dose	4 mg (N=5)	20 mg (N=5)	40 mg (N=3)	80 mg (N=5)	160 mg (N=5)
C max (ng/mL)	$198 \pm 89.1$	$1280 \pm 402$	$1650 \pm 257$	5120 ± 1410	$10300 \pm 4470$
AUC(0-t) (h*ng/mL)	74500 ± 247 00	430000 ± 9570 0	661000 ± 1580 00	1610000 ± 3170 00	3390000 ± 14500 00
AUC(0-∞) (h*ng/mL)	87100 ± 283 00	505000 ± 1050 00	804000 ± 1960 00	1850000 ± 3530 00	3990000 ± 18100 00
t 1/2 (h)	$245 \pm 9.50$	$249 \pm 6.08$	$255 \pm 43.1$	$235\pm22.8$	$243 \pm 40.4$
tmax (h)	96 (94.4 – 192)	96 (48. – 96.2)	120 (96 – 192)	96 (72 – 120)	120 (72 – 120)

Note: data are presented as means  $\pm$  standard deviation, except for tmax values, where the median is presented (minimum value – maximum value)

As can be seen from the presented table, the maximum concentration of RPH-104 appears in the blood on average approximately 4-5 days after the subcutaneous administration of RPH-104. The

CONFIDENTIAL P. 28 of 84

study results showed that RPH-104 at doses ranging from 4 to 160 mg has linear pharmacokinetics and its half-life is approximately equal to 10 days.

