# 4.6 Justification for the method of administration, dosing, dosing regimen, and treatment course

It is expected that in this study, subcutaneous administration of RPH-104 at doses from 4 to 160 mg may reduce pain intensity in patients with an acute gout attack.

The rationale for effective doses of RPH-104 is based on the following assumptions:

- 1. The blood IL-1β level in patients with gout does not exceed 100 pg/mL [11],
- 2. The blood IL-1β level in healthy volunteers is about 0.3 pg/mL [13].

CONFIDENTIAL P. 32 of 84

- 3. Dissociation constant of RPH-104 and IL-1β does not exceed 43.9 fM [7].
- 4. The molecular weight of RPH-104 is 152.7 kDa,
- 5. The molecular weight of IL-1β is 17.5 kDa.
- 6. The dissociation constant of RPH-104 and IL-1β relationship to the concentrations of RPH-104, IL-1β, and RPH-104:IL-1beta complex is described by the following equation:

$$Kd = \frac{[RPH-104]*[IL-1\beta]}{[RPH-104:IL-1\beta]}$$

where [RPH-104], [IL-1beta], and [RPH-104:IL-1 $\beta$ ] are the molar concentrations for RPH-104, IL-1 $\beta$ , and the RPH-104:IL-1 $\beta$  complex, respectively.

Thus, based on the above equation, the calculated concentration of RPH-104 in the blood capable of reducing the free blood IL-1 $\beta$  level from 100 pg/mL to 0.3 pg/mL is 20 pM or 3 ng/mL. It is expected that this concentration of RPH-104 may reduce pain in patients with gout.

According to a Phase 1 study in healthy volunteers, a blood concentration of RPH-104 of 3 ng/mL will be reached approximately 2 hours after subcutaneous injection of RPH-104 4 mg and less than 30 minutes after subcutaneous injection of RPH-104 20 mg and higher.

The results of the phase 1 study of RPH-104 showed that a single subcutaneous injection of RPH-104 at doses from 4 to 160 mg was well tolerated by healthy volunteers (see Section 4.3.3). Based on these results, it is assumed that RPH-104 will be well tolerated by patients following a single subcutaneous injection at doses ranging from 4 to 160 mg in this clinical study.

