Information about the investigational product used for the treatment of acute gout in the patients in this study (RPH-104 or Voltaren® (diclofenac)) and the dose of RPH-104 is unblinded to the patients and physicians. Patients who do not tolerate pain receive the rescue medication after 2 hours and until Day 45 of the study after the first use of rescue medication to intensify therapy. The rescue medication is triamcinolone 40 mg intramuscularly. If an attack recurred after the use of the rescue medication, treatment of acute gout attack is carried out in accordance with the standard practice of the hospital.

[figure not shown]
The primary efficacy variable is assessed 72 hours after initiation of the investigational product use. Secondary efficacy variables are evaluated over a 45 day period of therapy and follow-up.

[figure not shown]
The safety of the investigational product is assessed over a 60-day period of therapy and follow-up.

The study flow diagram is shown in Figure 6.1. The total duration of the study for one patient does not exceed 70 days.

RPH-104 4 mg once: n=15

CONFIDENTIAL P. 36 of 84

\* Screening procedures must be performed within 24 hours and the patient is randomized during this time. If necessary (in exceptional cases), the screening period can be extended, while randomization must be carried out no later than 120 hours (5 days) after the onset of an attack.

Figure 6.1 Flow diagram of the study design.

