#### Day 45 (1056 hours after the start of therapy)

- 12-lead ECG;
- Urinalysis;
- Dispensing questionnaires to the patient to record the following:
  - o Pain intensity in the assessed joint according to VAS;
  - o Patient global assessment of the efficacy using a categorical scale;
  - o Health assessment questionnaire completion.
  - o Blood sampling for the following analyses:
  - O Assessment of RPH-104 pharmacokinetics (only for patients randomized to the RPH-104 groups, central laboratory);
  - A study of anti-RPH-104 antibodies (only for patients randomized to the RPH-104 groups, central laboratory);
  - Complete blood count (local laboratory);
  - o Blood creatinine level (local laboratory);
  - Calculation of creatinine clearance (automatically in CRF using the Cockcroft-Gault formula);
  - Blood chemistry with blood lipids (central laboratory);
  - Blood clotting tests (central laboratory);
  - hs-CRP (central laboratory);
  - Serum amyloid protein A (central laboratory);
  - Cytokines (central laboratory);
  - o Serum pregnancy test for women of childbearing potential;

CONFIDENTIAL P. 57 of 84

- Assessment of the degree of swelling, tenderness, erythema and movement restriction in the assessed joint;
- Assessment of vital signs;
- Weighing;
- Physical examination;
- Evaluation of RPH-104 injection site reactions (only for patients who received RPH-104);
- Collecting information on concomitant therapy and adverse events;
- Patient diary collection and registration of entered data.

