# Day 60 ( $\pm$ 7 days)

On this day, the Investigator contacted the patient over the phone to collect information about adverse events, their characteristics (onset time, resolution time, severity, relationship to the investigational product, etc. as described in Section 12 of this protocol).

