# 12.1 Adverse event recording

Adverse events are registered either on the basis of complaints spontaneously reported by the patient or by the Investigator interviewing the patient or using physical examination findings and results of laboratory and instrumental investigations. The investigator should formulate his / her questions to the patient so that they do not prompt the patient to report unreliable information.

Adverse events should be registered in respective sections of the CRF, as well as in the patient's source medical documents.

Serious AEs are recorded from the time of signing the informed consent to participate in the study. All other adverse events will be registered beginning from the first dose of the investigational medicinal product. Adverse events will be registered until the end of the follow-up period. Reporting of serious AEs is described in section 12.5.

The following information should be reported for a registered adverse event:

- Patient ID
- Diagnosis of the adverse event (a diagnosis should be preferred to listing symptoms)
- The onset and resolution dates for the adverse event (and the times if applicable)
- AE severity
- Study drug relationship
- The measures that have been taken due to the adverse manifestation
- Actions taken in relation to the investigational drug
- Whether the adverse event meets the serious adverse event criteria

Adverse event outcome

CONFIDENTIAL P. 67 of 84

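### The treatment-emergent window in 13.6.1 stops 45 days after dosing, but adverse events are collected to Day 60, and the plan does not say where the later ones are counted

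*Combined protocol and SAP*

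**What the plan says.** Section 13.6.1 (Adverse events) defines two timing categories. Events from the start of administration "until 45 days after the investigational product administration will be considered treatment-emergent adverse events". Serious events between consent and administration are pre-treatment SAEs. There is no category for events that start after 45 days.

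The same section describes the main summary: "Frequency rates of adverse events during the study therapy will be calculated for each organ system". It adds severity, relatedness, withdrawal and SAE summaries, and gives no window for any of them.

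The collection period is longer:

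- Section 6.2: "The safety of the investigational product is assessed over a 60-day period of therapy and follow-up".
- Section 12.1: "Adverse events will be registered until the end of the follow-up period". Non-serious events are recorded from the first dose.
- Section 10.2, Day 60 (±7 days): "the Investigator contacted the patient over the phone to collect information about adverse events". Table 3.1 also marks AE recording at Day 60.

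Section 13.1 has all individual values listed. Section 13.1.7 leaves further detail to a separate statistical analysis plan, to be approved before the interim data lock. That plan is not part of the text reviewed here.

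**The concern.** The trial makes a call to collect AEs up to Day 60, but its one defined post-dose AE set closes about two weeks earlier, and no reason is given. The frequency table is tied to the period of study therapy. For RPH-104 that therapy is a single injection (9.5.3), so the phrase does not fix a window. Two programmers could fairly build different tables, one closing on Day 46 and one on Day 60.

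Safety is a stated objective (5.2), and the frequency and severity of AEs are named safety variables (6.1.5). At stake is whether non-serious events from the last part of follow-up appear in the main AE table. The timing matters because section 4 says that the interim report on 47 patients may become the final one.

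**Working it through.** **Inputs.** The window end is 45 days after administration (13.6.1). RPH-104 is given once, on Day 1. The last contact is on Day 60 ±7 days (10.2). Diclofenac is taken for 12 days (9.5.2). Mean half-life by dose is 235 to 255 h (Table 4.1).

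**1. Day numbering.** The heading of the last clinic visit begins "Day 45 (1056 hours after the start of therapy". With study day = hours/24 + 1, 1056/24 + 1 = 45, which agrees. The same rule reproduces all 11 scheduled post-dose days, from 24 h = Day 2 to 1056 h = Day 45.

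**2. End of the window for RPH-104.** 45 × 24 = 1080 h, and 1080/24 + 1 = Day 46.

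**3. Size of the gap.** Follow-up to Day 60 is 60 − 1 = 59 elapsed days.

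| Reading | Uncovered days | Share of elapsed follow-up |
|---|---|---|
| Literal, call on Day 60 | 60 − 46 = 14 | 14/59 = 23.7% |
| Literal, call on Day 53 | 53 − 46 = 7 | 7/52 = 13.5% |
| Literal, call on Day 67 | 67 − 46 = 21 | 21/66 = 31.8% |
| Window taken to end at the Day 45 visit | 60 − 45 = 15 | 15/59 = 25.4% |

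**4. Diclofenac.** The definition names the start of use for the opening of the window, but does not say which dose the 45 days run from. From the first dose, the window ends on Day 46 and the gap is 14 days. From the last dose, on about Day 12, it ends on Day 12 + 45 = Day 57 and the gap is 60 − 57 = 3 days (3/59 = 5%).

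**5. Is the late period relevant to RPH-104?** Section 4.3.2 says the drug "has linear pharmacokinetics and its half-life is approximately equal to 10 days". At 45 days, between 1080/255 = 4.2 and 1080/235 = 4.6 half-lives have passed, so simple halving from the time of dosing leaves about 4% to 5%. At Day 60 (59 × 24 = 1416 h) it is 5.6 to 6.0 half-lives, or about 2%. This is a rough count from healthy-volunteer means (3 to 5 subjects per dose) and ignores absorption time. The sponsor's own precautions on contraception (9.9) and live vaccines (9.8.5) run to 60 days after RPH-104.

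**6. With the window run to the Day 60 contact,** the uncovered time falls from 14 days to 0.

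**The case against.** The strongest reply is that nothing is shown to go missing. The term treatment-emergent is defined once and not used again, and no sentence restricts a table to that set. The Day 60 call sits under section 10.2, whose title covers the treatment period, so the therapy period in the frequency sentence could be read as reaching Day 60. The separate plan may already settle it. This stands: the undercount is conditional. It does not remove the point, because the other reading is just as open and the 45-day set is the only post-dose set defined.

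A second reply is that a cut-off near the last visit with laboratory tests, ECG and physical examination is defensible, since only a telephone call follows. That is fair as a reason for showing late events separately, but not for leaving their place unstated.

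Three stronger readings are tempting, and the documents support none of them.

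- **Late events are lost.** They are recorded (12.1) and listed (13.1). SAEs are summarised without a time limit, and the severity and relatedness summaries name no window.
- **The drug is still above its active level, so 45 days is unsafe.** Section 4.6 says the calculated concentration "is 20 pM or 3 ng/mL. It is expected that this concentration of RPH-104 may reduce pain in patients with gout". That is an efficacy estimate, and nothing makes it a safety threshold. The argument would also make Day 60 too short: at 4 mg, Table 4.1 gives 198 × 2^(−(1416 − 96)/245) = 4.7 ng/mL at Day 60, still above 3.
- **24% of AEs are affected.** The figure is a share of calendar time. The documents give no AE onset times.

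**Conclusion.** The mismatch is real and modest. For RPH-104 the treatment-emergent window closes on Day 46, while collection runs to Day 60. The 14 uncovered days are 24% of elapsed follow-up, or 13% to 32% across the call window. If the frequency table uses the defined set, non-serious AEs starting in that time are collected and listed but not counted in it. For diclofenac the gap is 14 or about 3 days, according to an anchor the protocol does not state. On the last-dose reading the arms would also be counted over different windows.

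This rests on the protocol text alone and on the literal reading of 45 days after dosing. The number of events affected cannot be estimated. The primary endpoint is untouched, and no bias between RPH-104 doses is claimed. It is a cheap improvement to consider, not a flaw that undermines the safety evaluation.

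**What to change.** In the SAP, before the interim data lock:

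- Base the AE frequency, severity and relatedness tables on all AEs with onset from first dose to the Day 60 contact, in every arm.
- Add one row by arm: patients with an AE starting more than 45 days after first dose.
- Count the 45 days from first dose in all arms, diclofenac included.

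This does not require changing the 45-day label. Events after it can be called follow-up AEs and tabulated as such, so the SAP and 13.6.1 do not conflict. Section 13.6.1 can be aligned at the next amendment, which needs approval under 16.4. If the interim report becomes final and no amendment follows, the follow-up category is sufficient by itself.

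The cost is one definition and one table row, with no new visit, call or data: the 47 interim patients have already completed participation (13.7). The downside is that late events rest on telephone recall. In the diclofenac arm, Days 47 to 60 also fall 35 to 48 days after the last tablet on about Day 12 (47 − 12 and 60 − 12), so attribution to treatment is weak there. The separate row makes both visible.
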